9. DISPOSITION AND WITHDRAWALS

Subject disposition will be summarized for the all enrolled population, by treatment group.

The number and percentage of subjects screened, screen failed, treated, completed and discontinued will be summarized, along with the primary reason for discontinuation.

Important protocol deviations will be identified programmatically and also manually, and will be subject to medical review as part of the Blind Data Review Meeting (BDRM) prior to database hard lock. Important protocol deviations will be summarized for the all enrolled population, by treatment group. This summary will be presented for all patients overall, and repeated by country.

Inclusion/exclusion criteria will only be listed for the all enrolled population, by treatment group.

The safety analysis population will be presented for the all enrolled population, by treatment.

10. DEMOGRAPHIC AND OTHER BASELINE CHARACTERISTICS

Demographic data and other baseline characteristics summaries will be presented for the safety population by treatment group. Listings will include all enrolled subjects.

No statistical testing will be carried out for demographic or other baseline characteristics.

Summaries will include subjects who completed the prior double-blind study and entered the long-term study, as well as subjects who did not participate in the prior double-blind study and entered the long-term study only. Demographics and baseline characteristics will be carried over from the prior double-blind study for subjects who completed the prior double-blind study.

The following demographic and other baseline characteristics will be summarized and listed. Data points denoted by * are reported in a listing only:

1) Demographics

- Age (years)
- Sex
- Race
- Ethnicity
- Height (cm)
- Country
- Weight (kg)
- Body Mass Index (BMI) (kg/m²)

2) Other Baseline Characteristics

- Baseline Mood Stabilizer

Document:	K:\DSP\SM-13496\RVA97109\Biostatistics\Documentation\SAP	Version Number:	1.0
Author:	[name]	Version Date:	20MAR2018

Template No: CS_TP_BS016 – Revision 3
Effective Date: 01May2012

Reference: CS_WI_BS005

Copyright © 2012 [REDACTED] All rights reserved.
The contents of this document are confidential and proprietary to [REDACTED]
reproduction is strictly prohibited.

Unauthorized use, disclosure or

- o Lithium (mmol/L)
- o VPA (mg/L)
- LT Baseline scores
 - o MADRS total score
 - o CGI-BP-S depression score
 - o CGI-BP-S mania score
 - o CGI-BP-S overall score
 - o YMRS total score

3) Disease data

- Date of initial onset of bipolar I disorder*
- Age at initial onset of bipolar I disorder*
- DSM-IV-TR diagnostic code (regarding severity/psychotic/remission specifiers) of the current major depressive episode or other current episode*
- Date of onset of the current episode*
- Presence or absence of characteristics of rapid cycling disease course
- Number of mood episodes for the consequent 12 months, by episode type
- Date of onset of the most recent major depressive, manic, mixed or hypomanic episode*
- Date of most recent hospital discharge if hospitalized because of major depressive, manic, mixed or hypomanic episodes*
- Number of hospitalizations due to bipolar I disorder (0, 1, 2 or more)
- Psychiatric disease other than bipolar I disorder; diagnosis, DSM-IV-TR diagnostic code, date of onset*

11. SURGICAL AND MEDICAL HISTORY

Medical History information summaries will be presented for the safety population by treatment group. Listings will include all enrolled subjects.

Summaries will include subjects who completed the prior double-blind study and entered the long-term study, as well as subjects who did not participate in the prior double-blind study and entered the long-term study only. Surgical and Medical History will be carried over from the prior double-blind study for subjects who completed the prior double-blind study.

- Medical History will be coded using **MedDRA Version 19.1**
 - o Medical History conditions are defined as those conditions beginning prior to screening which stop prior to/are ongoing at Screening
 - o Summarized by System Organ Class (SOC) and Preferred Term (PT)

Document: K:\DSP\SM-13496\RVA97109\Biostatistics\Documentation\SAP
Author: [REDACTED] Version Number: 1.0
Version Date: 20MAR2018

Template No: CS_TP_BS016 – Revision 3 Reference: CS_WI_BS005
Effective Date: 01May2012

Copyright © 2012 [REDACTED] All rights reserved.
The contents of this document are confidential and proprietary to [REDACTED]. Unauthorized use, disclosure or reproduction is strictly prohibited.

12. PSYCHIATRIC HISTORY

Psychiatric history results, including DSM-IV-TR bipolar subtype diagnosis, are recorded on the eCRF, and will be summarized for the safety population, by treatment group. Number and percent of subjects reporting each DSM-IV-TR subtype will be presented. Listings will include all enrolled subjects.

Summaries will include subjects who completed the prior double-blind study and entered the long-term study, as well as subjects who did not participate in the prior double-blind study and entered the long-term study only. Psychiatric history will be carried over from the prior double-blind study for subjects who completed the prior double-blind study.

The following will be summarized descriptively:

- Most recent / current Episode of Bipolar I Disorder
 - o Major depressive episode
 - o Manic episode
 - o Mixed episode
 - o Hypomanic episode
- Bipolar I disorder cycling within 12 month (0-3, 4-7 or ≥ 8)
- Psychotic features of bipolar I history
- Age at initial onset of bipolar I in years
- Duration of bipolar I from initial onset to screening in years
- Duration of bipolar I from onset of current episode to screening in weeks
- Number of prior hospitalizations for bipolar I disorder (0, 1, ≥ 2)
- Duration since discharge from last hospitalization for each type of episode to screening in months
- Number of mood episodes for the consequent 12 months, by episode type
- Subjects with other psychiatric disorders present

Incidence of other Current Psychiatric Diagnoses will be summarized by DSM-IV Code subtype for the safety population by treatment group.

13. CONCOMITANT MEDICATIONS

Concomitant medications summaries will be presented for the safety population and coded using **WHO Drug Dictionary Enhanced /WHO Herbal Dictionary v01DEC2013**. Listings will include all enrolled subjects.

Summaries will include subjects who completed the prior double-blind study and entered the long-term study, as well as subjects who did not participate in the prior double-blind study and entered the long-term study only.

ATC coding will be performed for the study, including screen failed subjects. Medications will be summarized using ATC level 3 coding and Preferred Term.

Document: K:\DSP\SM-13496\RVA97109\Biostatistics\Documentation\SAP
Author: [REDACTED] Version Number: 1.0
Version Date: 20MAR2018

Template No: CS_TP_BS016 – Revision 3 Reference: CS_WI_BS005
Effective Date: 01May2012

Copyright © 2012 [REDACTED] All rights reserved.
The contents of this document are confidential and proprietary to [REDACTED]. Unauthorized use, disclosure or reproduction is strictly prohibited.

See Appendix 2 for handling of partial dates for medications. In the case where it is not possible to define a medication as prior, concomitant, or post treatment, the medication will be classified as both prior and concomitant.

- 'Prior' medications are medications which started prior to the first dose of study medication in the long-term study (D1002002) or have a missing medication start date. If they are ongoing at the start of study medication then the medication will be classified as prior and concomitant. For subjects who completed the prior double-blind study, prior medications are medications recorded during the double-blind study prior to the first dose of study medication in the long-term study.
- 'Concomitant' medications are medications which:
 - o started prior to, on or after the first dose of study medication in the long-term study or have a missing medication start date
 - o AND ended on or after the date of first dose of study medication in the long-term study or were ongoing at the end of the long-term study.
- 'Post' medications are medications which started on the same day or after the end of study medication administration in the long-term study.

A summary of subjects with concomitant use of antiparkinson medication will be summarized by treatment group. Additional summaries will be produced categorizing medication categories related to Mood Stabilizers, Anxiolytics and Hypnotics.

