3.4.2 Safety variables

- Incidence of adverse events (AEs) and adverse drug reactions (ADRs)
- Incidence of extrapyramidal AEs and ADRs
- Proportion of patients with concomitant use of antiparkinson medication

- Change from baseline in the prior study (D1002001) and the present study (D1002002) in the Drug-Induced Extrapyramidal Symptoms Scale (DIEPSS) total score (except for the overall severity score) at the final assessment and at each assessment point
- Change from baseline in the prior study and the present study in the individual DIEPSS symptoms scores at the final assessment and at each assessment
- Change from baseline in the prior study and the present study in the serum prolactin concentration at the final assessment and at each assessment point
- Change from baseline in the prior study and the present study in the ECG parameter (QTc) at the final measurement
- Change from baseline in the prior study and the present study in the fasting blood glucose, HbA1c (NGSP), glycoalbumin, total cholesterol, LDL cholesterol, HDL cholesterol and triglycerides at the final measurement
- Change from baseline in the prior study and the present study in the body weight at the final measurement
- Laboratory measures and vital signs
- Proportion of patients with any instance of suicide attempt or suicidal ideation based on the Columbia Suicide Severity Rating Scale (C-SSRS)

Rationale

Extrapyramidal symptoms are the most common side effects associated with antipsychotics and usually treated with antiparkinson drugs. The DIEPSS²²⁾ is an evaluation scale for the extrapyramidal symptoms that are caused by drugs.

Antipsychotics are known to increase serum prolactin concentration²³⁾. Some atypical antipsychotics are known to influence glucose metabolism, lipid metabolism, and body weight. Some drugs affect cardiac rhythm (eg, QT interval prolongation).

The rate of suicide is high for bipolar disorder, and prevention of suicide is one of the important aspects in the treatment of bipolar disorder. The C-SSRS²⁴⁾ is a tool designed to systematically assess and track suicidal adverse events (suicidal attempts and suicidal ideation), and is able to comprehensively identify suicidal events while limiting the over-identification of suicidal behavior.

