5.3 Concomitant medications and therapies

The following information of all medication administered between Visit 0 and follow-up visit will be recorded in the eCRF:

- drug name
- drug type; antipsychotics, antidepressants, mood stabilizers, anxiolytics, hypnotics, antiparkinson drugs, or other
- daily dose (for antipsychotics and mood stabilizers only)
- route of administration
- start date
- stop date
- frequency (for antipsychotics and mood stabilizers only)
- indication

Table 5 shows the restriction on concomitant medications/therapies.

Table 5 Restriction on concomitant medications/therapies

	Screening Phase	Treatment Phase	Follow-up visit
CYP3A4 inhibitors and inducers	A	A	C
Clozapine	A	A	C
Fluoxetine, olanzapine and fluoxetine combination	A	A	C
Depot antipsychotics	A	A	C
Psychotropics (except for mood stabilizers, antiparkinson drugs, anxiolytics, and hypnotics)	B	A	C
MAO inhibitors	A	A	C
Other investigational drugs and post-marketing clinical study medication	A	A	A
Chinese herbal medication	A	A	C
Ginkgo Biloba extract, Kava Kava, St. John's Wort	A	A	C
Electroconvulsive therapy	A	A	C
Mood stabilizers	B	B	C
Medications for extrapyramidal symptoms	B	B	C
Anxiolytics	B	B	C
Hypnotics	B	B	C
Medications for complications	B	B	C

A, Prohibited; B, Restricted; C, No restrictions

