2.2. SAFETY OBJECTIVES

The following safety objectives will be analyzed throughout the study up to Week 28 outside Japan and Week 52 within Japan, unless otherwise specified:

- 1) Incidence of adverse events (AEs) and adverse drug reactions (ADRs)
- 2) Incidence of extrapyramidal AEs and ADRs
- 3) Proportion of subjects with concomitant use of antiparkinson medication
- 4) Change from baseline in the prior double-blind study (D1002001) and the present study (D1002002):
 - Drug-Induced Extrapyramidal Symptoms Scale (DIEPSS) total scores (except for the overall severity score)

Document:	K:\DSP\SM-13496\RVA97109\Biostatistics\Documentation\SAP	Version Number:	1.0
Author:	[REDACTED]	Version Date:	20MAR2018

Template No: CS_TP_BS016 – Revision 3
Effective Date: 01May2012

Reference: CS_WI_BS005

Copyright © 2012 [REDACTED] All rights reserved.
The contents of this document are confidential and proprietary to [REDACTED]. Unauthorized use, disclosure or reproduction is strictly prohibited.

- DIEPPS individual symptoms scores
 - Serum prolactin concentration
 - ECG parameter (QTc)
 - Fasting blood glucose, HbA1c (NGSP), glycoalbumin, total cholesterol, LDL cholesterol, HDL cholesterol and triglycerides
 - Body weight (kg)
- 5) Laboratory measures and vital signs
- 6) Proportion of subjects with any instance of suicide attempt or suicidal ideation based on the Columbia-Suicide Severity Rating Scale (C-SSRS)

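### SAP section 13 bounds Concomitant by the first dose only, so every Post medication also counts as Concomitant

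*SAP*

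**What the plan says.** SAP section 13 sets up three medication classes.

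- *Prior*: started before the first long-term dose, or start date missing. A drug still being taken when study medication starts is classed as both prior and concomitant.
- *Concomitant*: two conditions joined by AND. The first is that the drug "started prior to, on or after the first dose of study medication in the long-term study or have a missing medication start date". The second is that it ended on or after the first long-term dose, or was ongoing at the end of the long-term study.
- *Post*: the text reads "medications are medications which started on the same day or after the end of study medication administration in the long-term study".

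A fallback covers unclear cases. Where "it is not possible to define a medication as prior, concomitant, or post treatment, the medication will be classified as both prior and concomitant".

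The same section then calls for summaries of concomitant antiparkinson drugs, mood stabilizers, anxiolytics and hypnotics. The first of these is a named safety variable: "Proportion of patients with concomitant use of antiparkinson medication" in Protocol 3.4.2 and "Proportion of subjects with concomitant use of antiparkinson medication" in SAP 2.2. SAP 2.2 opens its list with a general limit: "The following safety objectives will be analyzed throughout the study up to Week 28 outside Japan and Week 52 within Japan, unless otherwise specified".

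On data collection, Protocol 5.3 states: "The following information of all medication administered between Visit 0 and follow-up visit will be recorded in the eCRF". The follow-up visit is 14 ± 7 days after completion or discontinuation (SAP 3.4).

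**The concern.** A table of concomitant medication is read as use during study treatment. Under section 13 the class has a lower limit (the drug must reach the first dose) but no upper limit. A drug first taken after the last tablet therefore qualifies.

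Such records should be expected. Protocol Table 5, with its key "A, Prohibited; B, Restricted; C, No restrictions", moves mood stabilizers, drugs for extrapyramidal symptoms, anxiolytics and hypnotics from B in the treatment phase to C at follow-up. These are the classes that section 13 tabulates. Protocol 6.2.1 also requires the final MADRS before any post-treatment antipsychotic or other psychotropic is begun, so it foresees such prescribing.

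At stake is the accuracy of four descriptive tables, one of which reports a named safety variable. Two programmers could also derive different counts from the same text, one following the literal rule and the other the apparent intention.

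**Working it through.** The plan gives no figure to reproduce; the check is of the classification logic.

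**1. The rules as written.** Let F and L be the first and last long-term dose dates, s the medication start and e its end. By definition F ≤ L and s ≤ e.

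- Concomitant: s may be any date or missing, AND (e ≥ F, or ongoing at study end).
- Post: s ≥ L.

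**2. Consequence.** If s ≥ L, then e ≥ s ≥ L ≥ F, so the second Concomitant condition holds. The first holds for every start date. Post is therefore wholly contained in Concomitant.

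**3. Enumeration for an illustrative subject.** Assume F = day 1 and L = day 196 (28 × 7). The latest follow-up is then day 196 + 14 + 7 = 217. Start days that meet Post run from 196 to 217, which is 22 values. Pairing each with every possible end day up to 217 gives 22 + 21 + … + 1 = 22 × 23 / 2 = 253 pairs. All 253 also meet Concomitant. A drug taken from day 195 to day 200 is Concomitant only, as it should be.

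**4. Whether another rule removes the overlap.**

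- *Fallback in section 13.* It applies only to drugs that cannot be classified. These drugs can be classified, in two ways, and no order of priority is given.
- *Week 28 and Week 52 limits* (Protocol 9.6.4, SAP 2.2 and 6.3.2). SAP 6.3.2 defines a subject-level cut-off date only for Japanese subjects who continue past Week 28. If all these limits are read as date cuts, they remove most of the completers' follow-up drugs. They do not help with early discontinuers. Someone whose last dose is on day 60, for example, has follow-up between day 67 and day 81, well inside 28 weeks.
- *Seven-day limit on post-baseline data* (SAP 6.2). That section mentions medications when it discusses baseline, and it closes post-baseline data 7 days after the last dose. Section 13 neither repeats nor cites the limit. If it does apply, drugs started from the last-dose day to 7 days later remain in both classes.
- *Partial dates* (SAP Appendix 2). Stop-date rule 6 resets an imputed stop date that precedes the start to the start date. A drug started after treatment thus still ends after F.

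**5. Test of the change under fix.** With Concomitant limited to s ≤ L (or missing) and Post changed to s > L, the 253 pairs divide cleanly. Start days 197 to 217 give 21 × 22 / 2 = 231 pairs, all Post only. The other 22 pairs, which start on day 196, are Concomitant only. 231 + 22 = 253, and none is in both classes. If the upper bound were added but Post left as it is, those 22 pairs would stay in both.

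**The case against.** The strongest reply is that this is a drafting gap and not an analysis error. Section 13 names post treatment as a class of its own, so an experienced programmer would probably keep it apart. Overlap is not forbidden in general, since prior and concomitant may coincide. SAP section 8 says that the supplied templates govern table content. Those templates are not among the documents, so the concomitant tables may already leave out Post drugs. All of this is fair and keeps the point minor. It does not remove it, because the written rule gives the wrong class and no sentence in the text corrects it.

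A second reply is that the last dose is not the only defensible end of the window. SAP 6.2 runs post-baseline data, and SAP 17.1 runs TEAEs, to 7 days after the last dose, and a drug given for a counted TEAE is reasonably shown beside it. This stands as a cost of the fix. A cut strictly before the last-dose date would also be too tight. Study drug is taken after the evening meal (Protocol 5.2.1), so a drug begun earlier that day precedes the final dose and belongs with on-treatment use.

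A reader might infer that the tables would show prohibited use, because mood stabilizers other than lithium and VPA are barred until study treatment ends (Protocol 5.3.2.1). The documents do not support that reading. Section 13 summarizes by ATC level 3 and preferred term without marking permitted or prohibited use. Important deviations are identified separately, with medical review (SAP section 9).

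**Conclusion.** The point holds as a minor error in a stated rule. As written, every Post medication is also Concomitant. Literal coding would add drugs started at or after the end of treatment to the antiparkinson, mood stabilizer, anxiolytic and hypnotic summaries. The error has one direction: it can add patients to those counts but cannot remove any. If the Week 28 and Week 52 limits are date cuts, it falls mainly on early discontinuers. If the 7-day limit in SAP 6.2 covers medications, the affected window is short.

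The size cannot be quantified. A reader might be tempted to take the 74% completion rate of the PREVAIL 2 study (Protocol 3.5), treat the remaining 26% as early discontinuers and apply a rate of new drug starts. But 26% belongs to another study, and the documents give no rate of starts after the last dose, so the answer would only restate the guess.

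No hypothesis, sample size or error rate is involved (Protocol 9.5.1, SAP 7.4). The conclusion rests on the text of section 13. Whether the final tables are affected also depends on the templates.

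**What to change.** In SAP section 13:

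1. Add to Concomitant: and started on or before the date of last study dose, or start date missing.
2. Change Post to: started after the date of last study dose.
3. State that Post medications are excluded from the concomitant summaries.
4. Flag in the listing any medication started 1 to 7 days after the last dose.

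This takes three wording changes and one listing flag, and no new data. The downside is that drugs started 1 to 7 days after the last dose leave the concomitant tables while TEAEs with onset in those days are still counted (SAP 17.1). The flag lets the two be reconciled. For serious events and deaths the TEAE window is 14 days, so the team may wish to extend the flag to match.

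One separate correction can be made at the same time, although it is not part of the argument above. Stop-date rule 5 in SAP Appendix 2 gives a continuing medication the date of the last double-blind dose. That date belongs to the prior study and does not exist for patients who were not in it. The rule should refer to a long-term-study date or leave the record as ongoing. The alternative in section 13 for drugs ongoing at study end probably protects concomitant status from this rule, but the SAP does not say so.

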- For patients who completed the prior study and who received antiparkinson drugs or other drugs for extrapyramidal symptoms at the initiation of the study treatment, the drugs will be continued without any dosage modification.
- For patients who did not participate in the prior study and who did not receive antiparkinson drugs or other drugs for the treatment of extrapyramidal symptoms at screening, drugs for extrapyramidal symptoms will be prohibited from screening until the initiation of the study treatment.
- For patients who did not participate in the prior study and who received antiparkinson drugs or other drugs for the treatment of extrapyramidal symptoms at screening, the drugs should be titrated down appropriately and terminated before the initiation of the study treatment.
- For all patients, if any extrapyramidal symptoms develop or worsen after the initiation of the study treatment, only one of the drugs listed in Table 6 may be used, within the dose range specified in the table. If the drug is not effective, the drug may be replaced by another drug among the drugs listed in Table 6. For akathisia, propranolol (≤ 120 mg/day), amantadine (≤ 300 mg/day), or one of the drugs listed in Table 6 may be used. If the above-mentioned drugs are not available at the study site, similar drugs at equivalent doses may be used with prior authorization of the medical monitor.
- For all patients, antiparkinson drugs and other drugs for extrapyramidal symptoms will be prohibited for prophylactic purposes.

Table 6 Permitted concomitant antiparkinson drugs

Drug	Daily total dose
Biperiden	≤ 16 mg
Trihexyphenidyl	≤ 10 mg
Benztropine	≤ 6 mg
Diphenhydramine	≤ 300 mg

(4) Anxiolytics

From the initiation of the study treatment to the end of the study treatment, only lorazepam (≤ 2 mg/day) can be used as needed for treatment of anxiety, agitation, irritation, and otherwise, but administration will be prohibited within 8 hours before assessment of the MADRS, CGI-BP-S, SDS, HAM-A, YMRS and C-SSRS. If lorazepam is not available at the study site, similar drugs at equivalent doses may be used with prior authorization of the medical monitor. If lorazepam is not effective, another anxiolytics may be used with prior authorization of the medical monitor.

(5) Hypnotics

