9.6.4 Concomitant medications

Numbers and percentages of patients with concomitant use of antiparkinson drugs, mood stabilizers, hypnotics, and anxiolytics will be summarized for all patients and by treatment group in the prior study. These summaries will be provided for overall (up to 28 weeks and up to 52 weeks, respectively).

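### The antiparkinson-use proportion mixes drugs carried over at Day 1 with drugs started on study, and the mixture differs between completers and new recruits

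*SAP*

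**What the plan says.** Protocol section 3.4.2 names as a safety variable the "Proportion of patients with concomitant use of antiparkinson medication". Section 9.6.4 asks for "Numbers and percentages of patients with concomitant use of antiparkinson drugs", for all patients and by prior treatment group, up to 28 and up to 52 weeks. SAP section 13 carries this out: "A summary of subjects with concomitant use of antiparkinson medication will be summarized by treatment group".

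The same SAP section sets what counts. A drug is concomitant if it "started prior to, on or after the first dose of study medication in the long-term study or have a missing medication start date", subject to a second condition, "AND ended on or after the date of first dose of study medication in the long-term study or were ongoing" when the long-term study ends. For a drug that spans Day 1 the rule is explicit: "If they are ongoing at the start of study medication then the medication will be classified as prior and concomitant".

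Protocol section 5.3.2.1 (3) then treats the two cohorts differently at entry. For completers on such a drug when study treatment begins, "the drugs will be continued without any dosage modification". For new recruits on one at screening, "the drugs should be titrated down appropriately and terminated before the initiation of the study treatment". After Day 1 one rule covers everybody: a permitted drug may be given when extrapyramidal symptoms appear or get worse, and prophylactic use is barred.

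**The concern.** Read together, these rules give one table row two meanings. A completer who arrives on an antiparkinson drug is counted as a user from Day 1, even if nothing extrapyramidal happens in this study. A new recruit cannot arrive on one if the stopping rule is followed, so a count in NR-LUR is essentially a new start. The exceptions are marginal, such as a stop date falling on Day 1 or a missing start date.

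This matters because the study is descriptive: the percentage is the result. A reader who sees a higher figure in LUR-LUR than in NR-LUR cannot tell how much comes from new treatment of symptoms and how much was present at entry. The completer columns share one entry rule, but carry-over may still differ between PBO-LUR and LUR-LUR, because it reflects treatment during the six-week prior study.

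The plan already makes this separation in its other extrapyramidal measures. TEAEs need an onset on or after the first dose of this study (SAP 17.1), and DIEPSS is also shown as change from LT baseline (SAP 17.7.1.2). The antiparkinson proportion has no counterpart.

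**Working it through.** The documents state no rate of antiparkinson use and no precision target for it, so there is no planned figure to reproduce. The check has two parts: who is counted, and how far the columns can diverge.

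**Who is counted under SAP 13**

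| Subject | Completer columns | NR-LUR |
|---|---|---|
| On a drug before Day 1 and kept on it | Counted | Should not occur (drug stopped before Day 1) |
| On a drug before Day 1, stopped before Day 1 | Not counted | Not counted |
| First started on study for symptoms | Counted | Counted |

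**How far the columns can diverge**

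Inputs from the documents: 325 completers and 80 new recruits planned (protocol 3.5), total 405. Assumed inputs:

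- c, the share of completers on an antiparkinson drug at Day 1, ranged over 0 to 15%
- u, the share of the remaining subjects who start one on study, ranged over 5 to 20% and taken as equal in both cohorts so that only the entry rule differs

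Formulas:

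- Completers: c + (1 − c)u
- New recruits: u
- Gap due to the entry rule: c(1 − u)
- ALL-EXT: [325 × (completer figure) + 80 × u] / 405

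For c = 5% and u = 10%:

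- Completers: 0.05 + 0.95 × 0.10 = 14.5%, against 10.0% in new recruits, a gap of 0.05 × 0.90 = 4.5 points
- ALL-EXT: (325 × 0.145 + 80 × 0.10) / 405 = 55.125 / 405 = 13.6%
- Carried-over share of completer users: 0.05 / 0.145 = 34%

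| c | u | Completers | NR-LUR | Gap (points) | ALL-EXT |
|---|---|---|---|---|---|
| 0% | 10% | 10.0% | 10.0% | 0 | 10.0% |
| 2% | 10% | 11.8% | 10.0% | 1.8 | 11.4% |
| 5% | 10% | 14.5% | 10.0% | 4.5 | 13.6% |
| 10% | 10% | 19.0% | 10.0% | 9.0 | 17.2% |
| 15% | 10% | 23.5% | 10.0% | 13.5 | 20.8% |
| 5% | 5% | 9.75% | 5.0% | 4.75 | 8.8% |
| 5% | 20% | 24.0% | 20.0% | 4.0 | 23.2% |
| 15% | 5% | 19.25% | 5.0% | 14.25 | 16.4% |

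Over the whole assumed range the gap runs from 0 to 14.25 points. Every row still contains new starts, so the completer figure is always a mixture.

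**Can the split be recovered from another planned table?** No. Prior medications, as SAP 13 defines them, also include drugs that ended before Day 1. The overlap of prior and concomitant cannot be read off two separate frequency tables.

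**The case against.** The SAP implements the protocol variable as written. Concomitant use means use during the study, and the protocol lists the incidence of extrapyramidal events as a separate variable. For someone treated with lurasidone in the prior study, a symptom that began there and still needs a drug belongs to the long-term burden. New symptoms are covered by extrapyramidal TEAEs and by DIEPSS change from LT baseline. There is no hypothesis, SAP section 17 plans no statistical comparison of treatment groups on safety, and NR-LUR has its own column and differs in other ways too (Japan only, mandatory lithium or VPA, a different index episode).

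Most of this stands. It means the protocol-defined proportion should not be replaced, and that the consequence is limited. It does not make the row interpretable. TEAEs and DIEPSS are different measures, and a symptom under treatment may score low on DIEPSS. The absence of tests does not help a reader of a descriptive percentage.

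A reader might infer that the variable reflects the entry rules instead of symptoms arising in this study. The documents do not support that: starts for symptoms that emerge or worsen on study count in every column. A reader might also infer that the completer figure is two to three times too high. That needs low new use and sizeable carry-over. At u = 5%, c = 5% gives 9.75 / 5 = 1.95 times and c = 10% gives 14.5 / 5 = 2.9 times. At u = 10% and c = 2% the ratio is 11.8 / 10 = 1.18, and at c = 0 it is 1. Nor is the planned figure too high as a measure of use, which is what the protocol names.

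**Conclusion.** The concern holds as a matter of interpretation. The planned proportion mixes carried-over and new use, the mixture depends on the cohort, and ALL-EXT pools the two. The definitions and the entry rules establish this without any assumption about rates, given that the stopping rule for new recruits is followed.

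The size is unknown. It rests on c, which the documents do not give and which could be near zero. The 4.5-point gap at c = 5% and u = 10% illustrates the mechanism and is not an estimate. This is one descriptive safety row with related measures beside it, so the correction is modest. It is still worth making, because without it nobody reading the table can tell which case applies.

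**What to change.** Keep the protocol-defined proportion in the SAP 13 antiparkinson summary. Add two rows, by treatment group, up to Week 28 and (Japan) up to Week 52:

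- **(a)** Subjects on an antiparkinson drug at Day 1.
- **(b)** Among subjects not on one at Day 1, those who first started one on or after Day 1 and not later than the last dose.

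Three details matter:

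- Restricting (b) to subjects not on a drug at Day 1 stops a carried-over user who switches between the Table 6 drugs from being counted as a new start.
- The upper limit is needed because SAP 13 sets no latest start date for a concomitant drug, while protocol section 5.3 records medication through the follow-up visit, when Table 5 lifts the restriction on these drugs.
- SAP Appendix 2 sets completely missing start dates, and some partial ones, to the first dose date, which could make a carried-over drug look new. Subjects whose start date was imputed in this way should not count in (b), and should be shown on a separate line.

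Start and stop dates are already collected in the eCRF, so the cost is a little extra programming. The new-use figure for completers will be smaller than the headline proportion wherever there is carry-over, and the report should say why. No medication rule changes.
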